4.1. Protocol Deviations

Important protocol deviations (including deviations related to study inclusion/exclusion criteria, conduct of the trial, patient management or patient assessment) will be summarised and listed.

Important deviations which result in exclusion from the analysis population will also be summarised and listed. (Please refer to [Appendix 1](#): Protocol Deviation Management and Definitions for Per Protocol Population).

Protocol deviations will be tracked by the study team throughout the conduct of the study in accordance with the Protocol Deviation Management Plan.

- Data will be reviewed prior to unblinding and freezing the database to ensure all important deviations and deviations which may lead to exclusion from the analysis are captured and categorised on the protocol deviations dataset.
- This dataset will be the basis for the summaries and listings of protocol deviations.

CONFIDENTIAL

200879

A separate summary and listing of all inclusion/exclusion criteria deviations will also be provided. This summary will be based on data as recorded on the inclusion/exclusion page of the eCRF.

5. CONSIDERATIONS FOR DATA ANALYSES AND DATA HANDLING CONVENTIONS

5.1. Study Treatment & Sub-group Display Descriptors

Treatment Group Descriptions			
RandAll NG Randomization System		Data Displays for Reporting	
Code	Description	Description	Order in TLF
A	Placebo	Placebo	1
B	GSK2269557 12.5 mcg	NEMI 12.5 mcg	2
C	GSK2269557 25 mcg*	NEMI 25 mcg	3
D	GSK2269557 50 mcg	NEMI 50 mcg	4
E	GSK2269557 100 mcg	NEMI 100 mcg	5
F	GSK2269557 250 mcg	NEMI 250 mcg	6
G	GSK2269557 500 mcg	NEMI 500 mcg	7
H	GSK2269557 750 mcg	NEMI 750 mcg	8

* The nemiralisib dose of 25 mcg may be added following the results of an un-blinded interim analysis if further characterization of the lower end of the dose response curve is required.

Treatment comparisons will be displayed as follows using the descriptors as specified:

1. NEMI 12.5 mcg vs Placebo
2. NEMI 25 mcg vs Placebo
3. NEMI 50 mcg vs Placebo
4. NEMI 100 mcg vs Placebo
5. NEMI 250 mcg vs Placebo
6. NEMI 500 mcg vs Placebo
7. NEMI 750 mcg vs Placebo

5.2. Baseline Definitions

For all endpoints, the baseline value will be the latest pre-dose assessment with a non-missing value, including those from unscheduled visits. If time is not collected, Day 1 assessments are assumed to be taken prior to first dose and used as baseline.

Post-bronchodilator Baseline FEV₁ is defined as the latest FEV₁ measured prior to the first dose of study treatment and post-bronchodilator.

CONFIDENTIAL

200879

Pre-bronchodilator Baseline FEV₁ is defined as the latest FEV₁ measured prior to the first dose of study treatment and pre-bronchodilator.

Baseline CAT Total Score is defined as CAT Total Score measured prior to the first dose of study treatment on Day 1.

Baseline SGRQ Total Score is defined as SGRQ Total Score measured prior to the first dose of study treatment on Day 1.

Unless otherwise stated, if baseline data is missing no derivation will be performed and baseline will be set to missing.

A centred baseline will be derived for each participant by subtracting the mean baseline across all participants from each participant's baseline value. The 'centred' baseline may be used instead of Baseline in the statistical analyses to aid convergence.

5.3. Multicentre Studies

In this multicentre global study, enrolment will be presented by investigative site and country.

5.4. Examination of Covariates and Subgroups**5.4.1. Covariates**

The list of covariates may be used in descriptive summaries and statistical analyses, some of which may also be used for subgroup analyses. Additional covariates of clinical interest may also be considered. The decision to include covariates in the model will be based on their impact on the model fit and will be detailed in the CSR.

A centred covariate will be derived for each participant by subtracting the mean covariate across all participants from each participant's covariate value. The 'centred' covariate may be used in place of the covariate in the statistical analyses to aid convergence.

CONFIDENTIAL

200879

Covariate	Details
Index exacerbation severity	Categorical variable (Moderate or Severe) derived using the stratification variable from the randomisation system.
Age (at screening)	Continuous variable derived as described in Section 13.6.2.1
BMI	Continuous variable derived using Height and Weight variables collected in eCRF: BMI = Weight (kg) / (Height (m)) ²
Gender	Categorical variable (Male or Female), collected in eCRF
Country	Categorical variable
Smoking status	Categorical variable (Current or Former), collected in eCRF
Baseline COPD maintenance therapy type	Categorical variable derived depending on data observed. Possible categories of interest are: Monotherapy vs. Dual therapy vs. Triple therapy
Index exacerbation type	Categorical variable: New or Relapse, derived using the question: "Other than the current prescription, for the index exacerbation, has the subject received oral/systemic corticosteroids and/or antibiotics for a COPD exacerbation within the last 7 days?" in the eCRF: New = No Relapse = Yes
Number of exacerbations in the previous 12 months	Categorical variable derived from "Total number of COPD exacerbations in the last 12 months" in the eCRF. Possible categories of interest are: 0 vs. 1 vs. ≥2

5.4.2. Examination of Subgroups

The list of subgroups may be used in descriptive summaries and statistical analyses. Additional subgroups of clinical interest may also be considered.

- If the percentage of subjects is small within a particular subgroup, then the subgroup categories may be refined.
- If the category cannot be refined further, then descriptive rather than statistical comparisons may be performed for the particular subgroup.

Subgroup	Categories
Index exacerbation severity	Moderate vs. Severe
Baseline COPD maintenance therapy type	Possible categories of interest are: Monotherapy vs. Dual therapy vs. Triple therapy
Index exacerbation type	New vs. Relapse
Number of exacerbations in the previous 12 months	Possible categories of interest are: 0 vs. 1 vs. ≥2
Gender	Male vs. Female
Smoking status	Current vs. Former

CONFIDENTIAL

200879

5.5. Other Considerations for Data Analyses and Data Handling Conventions

Other considerations for data analyses and data handling conventions are outlined in the appendices:

Section	Component
Section 13.2	Appendix 2 : Assessment Windows
Section 13.3	Appendix 3 : Study Phases and Treatment Emergent Adverse Events
Section 13.4	Appendix 4 : Data Display Standards & Handling Conventions
Section 13.5	Appendix 5 : Derived and Transformed Data
Section 13.6	Appendix 6 : Reporting Standards for Missing Data
Section 13.7	Appendix 7 : Values of Potential Clinical Importance

6. STUDY POPULATION ANALYSES

6.1. Overview of Planned Study Population Analyses

The study population analyses will be based on the “APE” and/or “MITT” populations, unless otherwise specified.

Study population analyses including analyses of participant’s disposition, protocol deviations, demographic and baseline characteristics, and exposure and treatment compliance will be based on GSK Core Data Standards. Details of the planned displays are presented in [Appendix 11](#): List of Data Displays.

6.1.1. Concomitant medications

Concomitant medications will be summarised by treatment group. Separate summaries of Baseline and On-treatment (Step-up) COPD Maintenance Therapy, and duration of OCS use will also be presented.

Additional summaries or sensitivity analyses of on-treatment COPD maintenance therapy (step-up therapy) may be performed if the data indicate that further investigation is warranted.

CONFIDENTIAL

200879

7. EFFICACY ANALYSES

Details of the outputs are provided in [Appendix 11: List of Data Displays](#) and will be based on GSK data standards and statistical principles.

Further details for use in the endpoint derivations below can be found in [Appendix 5: Derived and Transformed Data](#).

7.1. Primary Efficacy Analyses

7.1.1. Primary Endpoint

The primary endpoint of change from baseline in clinic visit trough FEV₁ at Day 84 measured post-bronchodilator is defined as:

FEV₁ measured prior to dosing and post-bronchodilator on Day 84 – Post-bronchodilator Baseline FEV₁

7.1.2. Primary Statistical Analyses

The primary endpoint will be analysed by fitting a suitable dose response model. The following models will be fitted, and the one that gives the best fit to the data will be selected: Bayesian 4-parameter E_{max} dose response model, 3-parameter E_{max} model and a Log-linear model.

The 4-parameter E_{max} dose response model will take the form:

$$\text{Change from baseline FEV}_1 = (E_0 + a_1 * \text{baseline}) + \frac{(E_{\max} + b_1 * \text{baseline}) * \text{Dose}^\gamma}{ED50^\gamma + \text{Dose}^\gamma}$$

The 3-parameter E_{max} dose response model will take the form:

$$\text{Change from baseline FEV}_1 = (E_0 + a_1 * \text{baseline}) + \frac{(E_{\max} + b_1 * \text{baseline}) * \text{Dose}}{ED50 + \text{Dose}}$$

Where: E₀ = the response at dose = 0 (placebo)

E_{max} = the maximal response

ED50 = the dose that yields 50% of the maximal response

γ = the slope parameter

a₁, b₁, are covariates for explanatory parameters

Initially, normal non-informative priors will be used for the E₀, a₁, a₂, and E_{max} parameters with mean 0 and standard deviation 1E6 L. A functional uniform prior will be used for the ED50 and slope parameters ([Bornkamp, 2014](#)), where the prior density for the functional uniform prior is based on all the parameters in the model. An inverse -

CONFIDENTIAL

200879

gamma prior with shape of 0.001 and scale of 0.001 will be used for the residual variance. However, if a prior distribution appears not to be truly non-informative then alternative prior distributions may be used.

Parameters will be blocked such that the MCMC procedure samples from E_0 , a_1 , b_1 , and E_{\max} , first, then the ED50 and slope parameters and then finally the residual variance parameter. For the functional uniform priors, the density will be calculated for values of dose from 0.0001 to 750 in steps of 50 (i.e. 0.0001, 50.0001, 100.0001, ..., 750.0001). For the continuous covariates, the density will be calculated from the minimum to the maximum in 10 equal steps. For binary covariates the density will be calculated for values 0 and 1. If the model does not converge including covariates, the model may be fitted with covariates removed.

If the log-linear model is fitted an offset of 1 will be used.

The posterior median change from baseline with 95% Highest Posterior Density (HPD) Credible Intervals, will be presented for each dose along with the adjusted median difference from placebo with 95% HPD, calculated at the mean baseline value across the treatment arms. Posterior probabilities that the true improvement is greater than 0 mL and 75 mL will also be presented. Graphical representation of the dose response across the full dose range will also be produced to allow inference to be made for the non-studied doses based upon the model fit.

For the futility analysis:

The predictive probability of success at the end of the study will be calculated (assuming the randomisation ratios remain the same after the interim) for each dose using the formula suggested by Spiegelhalter et al., 2004 as follows:

$$\text{Predictive probability} = 1 - \Phi \left[\frac{\sqrt{n_1}}{\sqrt{m_1}} z_{0.95} - \sqrt{\frac{n_1 + m_1}{m_1}} \frac{y_n}{\sigma} \right]$$

Where n_1 is the number of subjects with Day 84 data in the active arm of interest, m_1 is the number of subjects yet to be observed in the active arm of interest, y_n is the posterior mean difference from placebo from the fitted model, and σ is the standard deviation of the posterior mean difference from placebo.

For the possible adaptations at Interim Analysis 2:

If the study is not deemed futile, and either the 4 parameter or 3 parameter E_{\max} dose response curves has successfully been fitted to the data then adaptation of the randomisation schedule will be considered, to drop, add or amend doses from the randomisation scheme.

The adaptation will be done by comparing the relative information from alternative randomisation schemes with the original randomisation schemes, such to find the design that provides the most information about the dose response relationship. The efficiency ratio (ER) for an alternative scheme compared to the original, will be calculated as:

CONFIDENTIAL

200879

$$ER(\theta_i) = \left(\frac{|M(\xi_i, \theta_i)|}{|M(\xi_F, \theta_i)|} \right)^{\frac{1}{p}}, i=1, \dots, 1000$$

Where $M(\xi, \theta)$ is the information matrix for the design ξ and model parameters $\theta = (e\theta, emax, ed50, \gamma, a_1, b_1)^T$, ξ_1 is the alternative design one and ξ_F is the fixed original design, and p is the number of parameters (Dette et al 2008). In order to ensure any adaptation is robust to the variability in the parameter estimates at the interim analysis, 1000 samples will be generated from the posterior distribution of the parameters $\theta_1, \dots, \theta_{1000}$ and the ER calculated for each set of parameter. Adaptation will then only take place if the median ER is >1.05 and the 10th percentile of the ER is >1 . The efficiency ratio will be estimated using the mean baseline value across the population.

The alternative designs that will be considered will depend on the dose response model fitted but could include:

1. Add 25mcg dose
2. Add 25mcg dose, drop 500mcg dose
3. Add 25mcg dose, drop 250 mcg and 500 mcg doses
4. Drop 12.5mcg dose
5. Drop 12.5 mcg and 50mcg doses

The potential adaption may also be verified in the moderate and severe subgroups to ensure the adaption is beneficial across both groups.

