5.2. Baseline Definitions

For all endpoints, the baseline value will be the latest pre-dose assessment with a non-missing value, including those from unscheduled visits. If time is not collected, Day 1 assessments are assumed to be taken prior to first dose and used as baseline.

Post-bronchodilator Baseline FEV₁ is defined as the latest FEV₁ measured prior to the first dose of study treatment and post-bronchodilator.

Pre-bronchodilator Baseline FEV₁ is defined as the latest FEV₁ measured prior to the first dose of study treatment and pre-bronchodilator.

Baseline CAT Total Score is defined as CAT Total Score measured prior to the first dose of study treatment on Day 1.

Baseline SGRQ Total Score is defined as SGRQ Total Score measured prior to the first dose of study treatment on Day 1.

Unless otherwise stated, if baseline data is missing no derivation will be performed and baseline will be set to missing.

A centred baseline will be derived for each participant by subtracting the mean baseline across all participants from each participant's baseline value. The 'centred' baseline may be used instead of Baseline in the statistical analyses to aid convergence.

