5.4. Examination of Covariates and Subgroups

5.4.1. Covariates

The list of covariates may be used in descriptive summaries and statistical analyses, some of which may also be used for subgroup analyses. The key covariates of interest are Index exacerbation severity, Smoking history and Region. Additional covariates of clinical interest may also be considered. The decision to include covariates in the model will be based on their impact on the model fit and/or convergence and will be detailed in the CSR.

A centred covariate will be derived for each participant by subtracting the mean covariate across all participants from each participant's covariate value. The 'centred' covariate may be used in place of the covariate in the statistical analyses to aid convergence.

Covariate	Details
Index exacerbation severity	Categorical variable (Moderate or Severe) derived using the stratification variable from the randomisation system.
Age (at screening)	Continuous variable derived as described in Section 13.6.2.1
BMI	Continuous variable derived using Height and Weight variables collected in eCRF: BMI = Weight (kg) / (Height (m)) ²
Gender	Categorical variable (Male or Female), collected in eCRF
Country	Categorical variable
Region	Categorical variable derived using Country as: 
 • Americas: Canada, Mexico, United States • Asia: Australia, Korea • Eastern Europe: Poland, Romania, Russia • Western Europe: France, Germany, Italy, Netherlands, Spain, Sweden, U.K.
Smoking history	Categorical variable (Current or Former), collected in eCRF
Baseline COPD maintenance therapy type	Categorical variable derived depending on data observed. Possible categories of interest are: Monotherapy vs. Dual therapy vs. Triple therapy
Index exacerbation type	Categorical variable: New or Relapse, derived using the question: "Other than the current prescription, for the index exacerbation, has the subject received oral/systemic corticosteroids and/or antibiotics for a COPD exacerbation within the last 7 days?" in the eCRF: New = No Relapse = Yes
Number of exacerbations in the previous 12 months	Categorical variable derived from "Total number of COPD exacerbations in the last 12 months" in the eCRF. Possible categories of interest are: 0 vs. 1 vs. ≥2
Baseline COPD ICS therapy use	Categorical variable (ICS Use or Non-ICS Use) derived from review of concomitant medications

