7.1.2. Primary Statistical Analyses

The primary endpoint will be analysed by fitting a suitable dose response model. The following models will be fitted, and the one that gives the best fit to the data will be selected: Bayesian 4-parameter E_{max} dose response model, 3-parameter E_{max} model and a Log-linear model.

The 4-parameter E_{max} dose response model will take the form:

$$\text{Change from baseline FEV}_1 = (E0 + a_1 * \text{baseline}) + \frac{(E_{\max} + b_1 * \text{baseline}) * \text{Dose}^\gamma}{ED50^\gamma + \text{Dose}^\gamma}$$

The 3-parameter E_{max} dose response model will take the form:

$$\text{Change from baseline FEV}_1 = (E0 + a_1 * \text{baseline}) + \frac{(E_{\max} + b_1 * \text{baseline}) * \text{Dose}}{ED50 + \text{Dose}}$$

Where: E0 = the response at dose = 0 (placebo)

E_{max} = the maximal response

ED50 = the dose that yields 50% of the maximal response

γ = the slope parameter

a₁, b₁, are covariates for explanatory parameters

Initially, normal non-informative priors will be used for the E0, a₁, a₂, and E_{max} parameters with mean 0 and standard deviation 1E6 L. A functional uniform prior will be used for the ED50 and slope parameters ([Bornkamp, 2014](#)), where the prior density for the functional uniform prior is based on all the parameters in the model. An inverse -

gamma prior with shape of 0.001 and scale of 0.001 will be used for the residual variance. However, if a prior distribution appears not to be truly non-informative then alternative prior distributions may be used.

Parameters will be blocked such that the MCMC procedure samples from E_0 , a_1 , b_1 , and E_{\max} , first, then the ED50 and slope parameters and then finally the residual variance parameter. For the functional uniform priors, the density will be calculated for values of dose from 0.0001 to 750 in steps of 50 (i.e. 0.0001, 50.0001, 100.0001, ..., 750.0001). For the continuous covariates, the density will be calculated from the minimum to the maximum in 10 equal steps. For binary covariates the density will be calculated for values 0 and 1. If the model does not converge including covariates, the model may be fitted with covariates removed.

If the log-linear model is fitted an offset of 1 will be used.

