7.1.2.1. Model Checking & Diagnostics

The following list of convergence diagnostics will be applied for each parameter:

- The Monte Carlo Standard Errors (MCSE) should be compared with the standard deviation of the posterior distribution (SD) to ensure that only a fraction of the posterior variability is due to the simulation. The number of samples generated and/or the thinning may be increased to reduce the ratio of the MCSE/SD as deemed necessary.
- The Geweke diagnostic test will be used to assess whether the mean estimates have converged by comparing means from the early and latter part of the Markov chain using a z-score t-test. Large absolute values of the z-score statistic indicate rejection of the null hypothesis of no difference between the mean estimates obtained from the early and latter parts of the chain.
- Trace plots of samples versus the simulation index will be visually inspected to assess some aspects of convergence. The centre of the chain should appear stable with very small fluctuations, i.e., the distribution of points should not change as the chain progresses and the posterior mean and variance are relatively constant.
- Autocorrelation plots will be visually inspected to assess degree of autocorrelation (should decline rapidly and show no oscillation patterns).

CONFIDENTIAL

200879

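### Section 7.1.2 ranks dose-response models by fit but lets a non-converging one drop its baseline terms, with no rule that ranked models share covariates

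*SAP*

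**What the plan says.** The references are to the current SAP; an earlier SAP text in the same file has the same sentences.

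- **Selection.** Section 7.1.2 lists a 4-parameter Emax, a 3-parameter Emax and a log-linear model: "The following models will be fitted, and the one that gives the best fit to the data will be selected". No fit criterion is tied to this. AIC appears only in the abbreviation list.
- **Covariates in the model.** Both Emax equations carry a1 × baseline in the placebo response and b1 × baseline in the maximal effect. The SAP says of a1 and b1 that they "are covariates for explanatory parameters". For the log-linear model it gives no equation, only this: "If the log-linear model is fitted an offset of 1 will be used".
- **Fallback.** "If the model does not converge including covariates, the model may be fitted with covariates removed".
- **General rule.** Section 5.4.1: "The decision to include covariates in the model will be based on their impact on the model fit and/or convergence", with the decision to be reported in the CSR.
- **Centring.** Section 5.2 makes it optional: the centred "baseline may be used instead of Baseline in the statistical analyses to aid convergence".
- **Outputs that presuppose baseline.** Section 7.1.2 evaluates the adjusted difference from placebo at the average baseline over the arms. It also lists a1 and b1 in the parameter vector of the efficiency ratio used at Interim Analysis 2.

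**The concern.** A fit comparison tells us about dose shape only if the models differ in dose shape alone. The fallback is worded for a single model, and no section says that the other candidates must follow when one is reduced. An Emax curve without baseline could therefore be ranked against a curve that has it. Two different harms can follow, and they are alternatives:

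1. Baseline is prognostic, so the reduced curve loses the ranking for a reason unrelated to dose. The selected model keeps its baseline adjustment but may have the wrong shape.
2. The reduced curve wins, or every candidate is reduced. The primary contrasts are then unadjusted. They lose precision and carry any chance baseline imbalance, and there is no baseline term left for the planned reporting at mean baseline to act on.

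The stated primary objective is to characterise the dose response. The chosen curve supplies the dose estimates, the inference at unstudied doses, and the posterior mean and SD that enter the first futility step. Adaptation at Interim Analysis 2 also requires that an Emax curve was fitted successfully, and the SAP does not say whether a stripped fit counts.

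**Working it through.** The SAP gives no figure to reproduce, so the check compares the fit value of the baseline term with the fit value of dose shape.

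**Inputs.** From the SAP: the three models, the fallback, the offset of 1, and about 300 participants with Day 84 data at Interim Analysis 2 (section 3.1). Assumed, because the SAP does not give them: AIC as criterion, final n of 900 to 1000, allocation 3:1:1:1:1:1:3, residual SD 0.24 L, Emax 0.10 to 0.15 L, ED50 25 to 100 mcg, and correlation ρ between baseline and change of size 0 to 0.4.

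**Step 1: value of the baseline term.** Deviance gain = −n ln(1 − ρ²). Under AIC, subtract 4 for the two parameters a1 and b1.

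| ρ | n=300 | n=900 |
|---|---|---|
| 0.1 | 3.0 | 9.1 |
| 0.2 | 12.3 | 36.7 |
| 0.3 | 28.3 | 84.9 |

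The same quantity can be written with the correlation r between baseline and Day 84 FEV1. With equal SDs, ρ² = (1 − r)/2, so the gain is n ln(2/(1 + r)). For r = 0.9, 0.8 and 0.7 it is 51, 105 and 163 at n=1000, and 15, 32 and 49 at n=300. These r values correspond to ρ of about 0.22 to 0.39 in size.

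**Step 2: value of dose shape.** Data were simulated from a true 3-parameter Emax (600 runs per setting, least-squares fits), with Emax and log-linear both adjusted for baseline. The absolute deviance difference had a median of 0.9 to 1.6 and a 95th percentile of 3.5 to 7.1 at n≈300. At n=900 these were 1.3 to 3.3 and 4.2 to 10.7. At ρ = 0.2 the baseline term (12.3 and 36.7) exceeds both upper percentiles.

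**Step 3: effect on selection.** Share of runs in which the true Emax was chosen:

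| Comparison | n≈300 | n=900 |
|---|---|---|
| Both with baseline, any ρ | 19–41% | 28–69% |
| Emax stripped, ρ=0 | 74–76% | 78–84% |
| Emax stripped, ρ=0.1 | 40–47% | 12–23% |
| Emax stripped, ρ=0.2 | 4–6% | 0% |
| Emax stripped, ρ≥0.3 | 0% | 0% |

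With common covariates the result shows no clear dependence on ρ. In the mixed comparison ρ drives it, and near zero the parameter penalty favours the stripped model.

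**Step 4: cost if an unadjusted fit is reported.** The information lost without a1 is (1 − r)/2, which is 5% to 15% for r = 0.9 to 0.7.

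**Step 5: direction of low-dose error if log-linear is chosen wrongly.** Log-linear fixes the 12.5 mcg effect at ln(13.5)/ln(751) = 39% of the 750 mcg effect. An Emax curve gives [12.5/(12.5 + ED50)] ÷ [750/(750 + ED50)]: 7% for ED50 = 200, 39% for ED50 = 20 and 46% for ED50 = 15. The error can therefore be upward, nil or downward.

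**The case against.** - **The sentence may not be meant for baseline.** It directly follows a remark on binary covariates, and the covariate table in section 5.4.1 does not list baseline FEV1. The outputs that presuppose baseline point the same way. This makes the wording ambiguous but does not settle it, because section 7.1.2 itself calls a1 and b1 covariates.
- **The mixed comparison is not prescribed.** This stands. The fallback is optional, and a careful analyst could refit all candidates alike. The SAP does not require it.
- **There is mitigation.** Centring is available, covariate decisions go into the CSR, and the supportive repeated measures analysis (section 7.1.3) keeps baseline-by-Day. This also stands, but centring need not be tried before removal, and a supportive model does not repair the choice of primary curve.
- **The calculation is conditional.** The simulation imposed the loss of baseline instead of waiting for convergence to fail, and it left out the 4-parameter Emax. It shows what a mixed comparison does, not how often one would occur.

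A reader might also infer that the fallback removes the wrong term, because a linear main effect cannot hinder convergence. That does not hold here. The fit is by MCMC, where an uncentred baseline makes E0 and a1 strongly correlated and slows mixing, and section 5.2 itself offers centring as an aid.

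**Conclusion.** The concern holds as a gap in the primary model-selection rule. The text lets one candidate lose baseline and still be ranked against candidates that keep it. From a baseline-change correlation of about 0.2, the baseline term then outweighs typical shape differences at n of 300 to 1000. Below that, the parameter penalty can tip the choice the other way. This rests on AIC as a stand-in and on assumed SD, effect, ED50, allocation and final n; the frequency of non-convergence is unknown.

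Four stronger readings are not supported:

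- That baseline will pick the model and adjustment will also be lost. These are alternative outcomes, and both are only permitted.
- That the log-linear model is known to keep baseline. This is inferred, since no equation is given.
- That low doses would be overstated. The direction depends on the true ED50, and the bias vanishes near 20 mcg.
- That the mock shells fix the allocation. Shell 35 shows 300/100/100/100/100/300 with no 12.5 mcg arm and Shell 3 shows 200 per arm, so they are placeholders.

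This is a cheap improvement worth making, not an error that invalidates the analysis.

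**What to change.** Replace the fallback sentence in section 7.1.2 with:

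> If a model does not converge, centred baseline is used first. If it still does not converge, b1 (baseline by dose effect) is removed from all candidate models and they are refitted. The main effect a1 × baseline is kept in every candidate. Fit is compared only between models with the same covariates and the same participants.

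If b1 is removed, the parameter list in the efficiency ratio should match the fitted model. Discarding any curve that still fails, or judging convergence on log(ED50), would be optional and is not needed for this point.

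The cost is a few sentences of SAP text and a few extra model fits, with no new data.
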